Project Title

Synergizing home health rehabilitation therapy to optimize patients' activities of daily living

Investigators

PI: [name], OTR/L, FGSA, UF Department of Occupational Therapy

CO-I: [name], PT, UF Department of Physical Therapy

CO-I: [name], UF Department of Biostatistics

Conflict of interest

All the investigators declare no conflict of interest.

Clinical Trial Registration #: NCT05411393

UF IRB202102816

Supported by the National Institute on Aging (R21 AG076972)

Date: 1/30/2024

Abstract

Regaining the ability to take care of oneself after an illness or medical episode is critical for older adults to maintain independent living at home in the community. Each year, 3 to 4.5 million older adults receive home health care services that provide skilled rehabilitation therapy in their home. These patients experience reduced capacity to perform activities of daily living (ADL) independently, which is a significant risk factor for long-term care placement. Recent data has shown that nearly 40% of home health patients do not improve in ADL at discharge. There is currently a lack of evidence-based rehabilitation programs in home health. Increasing activity-based intervention in home health care rehabilitation could be the key to improve patients' ADL independence. The objective of this study is to pilot test an ADL-enhanced program as an adjuvant therapy to usual home health rehabilitation to improve patients' ADL outcome. The ADL-enhanced program facilitates patients' participation in ADL first by lowering the task demand using a compensatory approach. As the patient increases physical capacity, the ADL-enhanced program shifts to a restorative approach, which increases the task demand to help the patient channel the improved physical capacity to better activity performance. Our specific aims were to: 1) estimate the preliminary effect of the ADL-enhanced program on improving ADL; 2) estimate the preliminary effect of the ADL-enhanced program on improving physical functioning of the upper extremity and the lower extremity; and 3) assess the program completion rate, satisfaction rate, and adverse event rate (e.g., falls and hospital admissions).

Study Objectives

Primary Objective.

The primary objective is to estimate the preliminary effect of the activities of daily living (ADL)-enhanced program on improving ADL at treatment completion, one month, and 3 months after the completion.

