Hypothesis: Patients who receive the ADL-enhanced program plus usual rehabilitation therapy will show greater improvements in the Motor Skills scores of the Assessment of Motor and Process Skills (the primary outcome), Self-care items in the Outcome and Assessment Information Set (clinical outcome), and Activity Measure for Post-Acute Care Home Health Short Form (patient-reported outcome) at treatment completion and less decline at 1-month and 3-month follow-up than usual rehabilitation therapy.

Secondary Objectives.

Secondary objective 1: To estimate the preliminary effect of the ADL-enhanced program on improving physical functioning at treatment completion and one month after the completion.

Hypothesis 1: Patients who receive the ADL-enhanced program plus usual rehabilitation therapy will show greater improvements in the Box and Block Test (upper extremity physical function), Jebsen Hand Function Test (upper extremity physical function), Timed-Up-and-Go Test (lower extremity physical function), and Short Physical Performance Battery (lower extremity physical function) at treatment completion and less decline at one-month follow-up than usual rehabilitation therapy.

Secondary objective 2: To assess the completion, satisfaction, and adverse event rates of the ADL-enhanced program.

Hypothesis 2a: We hypothesize that the program completion and satisfaction rates will be greater than 75%.

Hypothesis 2b: Fewer patients who receive the ADL-enhanced program will have hospitalizations, emergency room visits, and falls than patients who receive usual rehabilitation therapy at 1-month and 3-month follow-up.

Background and Rationale

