Study design overview. This is a single-blinded, pilot randomized controlled trial of 48 Medicare patients referred to HHC for skilled rehabilitation services. Twenty-four patients will be randomly assigned to the treatment-as-usual arm and receive usual rehabilitation services. The other 24 patients in the experimental arm will receive the ADL-enhanced program in six OT visits as well as usual rehabilitation services.

Selection and Enrollment of Participants

Participants will be recruited from partnered home health agencies

Inclusion criteria. Patients are eligible to the study if they are:

- (1) \geq 65 years of age,
- (2) Medicare beneficiaries,
- (3) referred for skilled rehabilitation services; and
- (4) diagnosed with three or more comorbidities.

Exclusion criteria. Patients are ineligible if they have contraindications for moderate-intensity exercise, which include:

- acute fractures with surgical or weight-bearing restrictions,
- elective joint replacement surgery,
- lower extremity amputation,
- active treatment for cancer diagnosis,
- on-going dialysis treatment,
- acute cardiac surgery,
- acute stroke or a major neurologic disorder limiting motor movements,
- terminal stage of congestive heart failure,
- a referral to hospice care, or
- severe cognitive deficits limiting verbal communication.

Enrollment Procedures.

Screening procedure. The home health care team will obtain verbal permission from new patients to allow the research coordinator to contact and screen the new patients via phone. The coordinator will record the screening results (fail or pass) on a screening log. The coordinator will call the eligible patient, verify the eligibility, and introduce the study.

Consent procedure. The coordinator will then conduct a recruitment home visit to the eligible patient and obtain consent at the end of the visit. If the patient does not provide consent during the recurrent home visit but decides to participate in the study afterwards, a study outcome assessor will obtain consent at the beginning of the baseline assessment visit. Reasons of rejection will be recorded.

Patients who are eligible and agree to participate will be referred to the study outcome assessor, who will schedule the patient within 48 hours to obtain the consent, if not yet obtained by the research coordinator, and complete the baseline assessments (ADL and physical functioning assessments) at the participant's home. The assessor will be blinded to group assignments.

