3. Jebsen Hand Function Test
4. Box and Block Test
5. Timed-Up-and Go
6. Short Physical Performance Battery
7. Adverse events questionnaire

Final evaluation or three-month follow-up evaluation.

The final evaluation will occur over the phone by the research assistant or coordinator within seven days three months after the completion of the last visit of usual home health rehabilitation therapy or ADL-enhanced intervention (Day 90 post intervention). The following assessments will be administered during the final evaluation.

1. Activity Measure of Post-Acute Care Home Health Short Form
2. Adverse events questionnaire

Data analysis plan.

Preliminary analysis. We will compare participant demographics and covariates (e.g., pain levels) between the two groups. Variables with statistically significant differences will be included in the subsequent statistical models as covariates. We will graph spaghetti plots for repeated measurements and examine for outliers.

Data analysis. Since ADL and physical functioning outcomes will be collected over three time points (baseline, post-treatment, one-month follow-up), the mixed-effects linear regression modeling will be conducted to fit the data, in which a random-effects term is included to accommodate within-subject data correlation and a quadratic growth curve is included to describe the temporal trend of the response.

For **Aim 1**, which will estimate the preliminary effect of the ADL-enhanced program on improving ADL, three separate mixed-effects regression analyses will be conducted for the Motor Skills scores of the Assessment of Motor and Process Skills (the primary outcome), the Activity Measure of Post-Acute Care Home Health Short Form, and the OASIS self-care items, in each of which sex, race, age, and other covariates will be included in the model.

For **Aim 2**, which will estimate the preliminary effect of the ADL-enhanced program on physical functioning of the upper extremity and lower extremity, four similar separate analyses will be conducted for the Box and Block Test, Jebsen Hand Function Test, Timed-Up-and Go, and Short Physical Performance Battery.

For **Aim 3**, the program completion rate and satisfaction rate will be compared to the benchmark, 75%. Fisher's Exact Test will be performed to compare the proportion of patients who experience adverse events of hospitalization, emergency room visits, or falls (adverse event rate) between the two groups.

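### Aim 3 plans only a Fisher p-value for the between-arm comparison of adverse events; a risk difference with a 95% interval should be the main result

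*Combined protocol and SAP*

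**What the plan says.** The Study Design section sets the size: "This is a single-blinded, pilot randomized controlled trial of 48 Medicare patients referred to HHC for skilled rehabilitation services", with 24 patients in each arm. Secondary objective 2 is "To assess the completion, satisfaction, and adverse event rates of the ADL-enhanced program". Hypothesis 2b is directional: "Fewer patients who receive the ADL-enhanced program will have hospitalizations, emergency room visits, and falls than patients who receive usual rehabilitation therapy", at the 1-month and 3-month follow-ups.

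For this objective, Aim 3 in the data analysis plan compares completion and satisfaction with a 75% benchmark. For adverse events it states that Fisher's "Exact Test will be performed to compare the proportion of patients who experience adverse events of hospitalization, emergency room visits, or falls" between the groups. It names no risk difference, risk ratio or interval for that comparison. It also gives no significance level and does not say whether the test is one- or two-sided. The only mention of significance in the plan concerns covariate selection: "Variables with statistically significant differences will be included in the subsequent statistical models as covariates". No expected event rate appears anywhere.

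**The concern.** Aims 1 and 2 are worded as estimating a preliminary effect. The adverse event part of Aim 3 is the exception: its one planned between-arm output is a test. In a pilot, the useful product is the size of the difference and its uncertainty, because that is what the planners of a later trial need. They would want it in both directions. Hypothesis 2b expects fewer events, but the program adds moderate-intensity graded activity for older patients with three or more comorbidities, so an excess of falls or admissions also has to be sized. With 24 per arm, a non-significant p-value is likely under most plausible truths and separates none of them.

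A secondary matter is efficiency. Fisher's test conditions on the total number of events, which makes it conservative in small samples. Other exact tests hold the same nominal level with less loss.

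**Working it through.** **Inputs.** From the documents: 24 per arm and Fisher's exact test on the proportion of patients with an event. Assumed, because the documents are silent: a two-sided 5% level, all event rates, and the example counts. The plan gives no power or precision figure for adverse events, so there is nothing to reproduce first.

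**Step 1: what the p-value leaves out.** Take 10/24 on the program and 5/24 on usual care, a doubling. Fisher's two-sided p is 0.21. The Wilson limits for each arm are

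[p + z²/2n ± z√(p(1−p)/n + z²/4n²)] / (1 + z²/n), with z = 1.96 and n = 24.

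- Program: p = 0.4167, limits 0.2447 and 0.6117.
- Usual care: p = 0.2083, limits 0.0924 and 0.4047.

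Newcombe's interval for d = 0.4167 − 0.2083 = 0.2083 is then:

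- Lower: 0.2083 − √[(0.4167 − 0.2447)² + (0.4047 − 0.2083)²] = 0.2083 − 0.2610 = −0.053
- Upper: 0.2083 + √[(0.6117 − 0.4167)² + (0.2083 − 0.0924)²] = 0.2083 + 0.2268 = 0.435

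So the result is +21 points, 95% interval −5 to +44. The interval shows that a small benefit and a very large excess are both compatible with the data. The p-value shows neither.

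**Step 2: how far this extends.** Fisher's p for other exact doublings, usual care against program, out of 24 each: 3 v 6, 0.46; 4 v 8, 0.32; 6 v 12, 0.14; 7 v 14, 0.080; 8 v 16, 0.042. A doubling is therefore non-significant up to 7 v 14. At 7 v 14 the Newcombe interval is +1 to +52 points.

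**Step 3: what another exact test would change.** All 25 × 25 outcome tables were enumerated. Size is the rejection probability maximised over a common event rate, and power is the sum of binomial probabilities over the rejecting tables. Boschloo's p-value is the maximum, over the common rate, of the probability of a Fisher p at least as small as the one observed. At 24 v 24 the maximum size is 2.9% for Fisher and 4.9% for Boschloo.

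| Assumed rates | Fisher power | Boschloo power | Gain (points) |
|---|---|---|---|
| 20% v 10% | 9.7% | 11.2% | 1.5 |
| 30% v 15% | 16.1% | 20.2% | 4.1 |
| 40% v 20% | 23.6% | 30.6% | 7.0 |
| 50% v 25% | 33.7% | 43.3% | 9.6 |
| 50% v 20% | 49% | 59% | 10 |

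For the doublings in Steps 1 and 2, Boschloo gives p = 0.13 for 5 v 10 and 0.082 for 6 v 12. Among the non-significant ones, only 7 v 14 changes side (p = 0.049).

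**Step 4: dependence on equal arms.** At 23 v 24, Fisher's maximum size is 4.0% and the Boschloo gain is about 0 to 3 points over the same rates (50% v 20%: 55.1% to 57.8%). At 22 v 26 the maximum size is 4.2%. With equal loss, 22 v 22, it is 2.4%.

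**Step 5: the role of sample size.** For 80% power at two-sided 5%, n per arm = [1.96√(2p̄(1−p̄)) + 0.8416√(p₁(1−p₁) + p₂(1−p₂))]² / (p₁ − p₂)², where p̄ is the mean of p₁ and p₂. For 50% v 25% this is (1.342 + 0.557)² / 0.0625, or 58. For 20% v 10% it is (0.990 + 0.421)² / 0.01, or 199. The trial has 24.

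**The case against.** Fisher's test is a valid, conventional choice for a small two-by-two table, and this is one secondary hypothesis in a pilot. The aim is to assess rates and the test compares proportions, so per-arm rates are implied and a reader could subtract them. All of that stands. What subtraction does not supply is the uncertainty of the difference, and no interval for it is specified.

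Three stronger readings are tempting, and the documents do not support them.

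- A reader might infer that the test always runs below 3%. That figure belongs to 24 v 24 and other equal splits examined, at an assumed 5% level. One missing patient raises it to 4.0%, and the numbers analysed at follow-up are unknown.
- A reader might infer that the choice of test is why a real reduction would be missed. Most of the low power comes from the sample size: Boschloo's own power for a halving from 20% to 50% is only 11% to 43%. The larger gains also require assumed control rates of 40% to 50%.
- A reader might infer that the investigators will present a non-significant result as evidence of safety. No section says so; the comparison is framed as a hypothesis of benefit. A statement against that interpretation is a precaution, not a correction of something written.

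**Conclusion.** The point holds as an inexpensive improvement, not as an error that invalidates the analysis. Aim 3 specifies a test where its objective calls for an estimate, and at 24 per arm the gap is material: in the illustrative doubling, p = 0.21 accompanies an interval nearly 49 points wide (−5.3 to +43.5). This conclusion needs no assumption about the true event rates, because it rests only on the missing interval and the planned arm sizes; the example counts are illustrative.

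The choice between Fisher and Boschloo is secondary and optional. Boschloo's test holds the nominal level and is never less powerful than Fisher's, but its advantage is uneven: about 1.5 to 10 points at 24 v 24 and about 0 to 3 at 23 v 24. These figures depend on an assumed two-sided 5% level and assumed event rates. Changing the test does not make the 5 v 10 doubling significant; only the interval describes it adequately.

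**What to change.** In Aim 3, state that the main adverse event result is the risk difference (program minus usual care) with a 95% Newcombe or Miettinen-Nurminen interval, shown beside the counts and proportions per arm at the follow-up times named in Hypothesis 2b. Add that a non-significant difference will not be interpreted as equal safety.

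If a test is also reported, state its level and sidedness. Boschloo's exact test may replace Fisher's. If Fisher's is kept, say in advance that the interval leads, because the two can disagree: at 7 v 14 Fisher's p is 0.080 while the Newcombe interval excludes zero.

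The cost is a few sentences in the plan, a line or two of code and slightly more reporting. The data are already collected. The one drawback of the optional part is a less familiar test name.
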